- m If applicable, Visit 7 or Visit 6 should be used to inform Group B transplant subjects (Cohort 13 of the BNT162-01 trial) on Dose 2 and informed consent must be collected. If Visit 6 is applicable, then Visit 7 must be skipped. Thereafter the SoA in Table 2a is applicable.
- n Record any non-trial SARS-CoV-2 vaccinations that trial subjects receive during the trial in the CRF until the last trial visit.
- o If a transplant subject consents to receive a second vaccination (i.e., 4th dose since the parent trial), the SoA in Table 2a is then applicable, there will be no blood sampling for CMI testing at the visit of consent (Visit 6 or Visit 7).
- p Only for Group B transplant subjects: record any non-trial SARS-CoV-2 vaccinations that trial subjects receive in the CRF.

Abbreviations: AE = adverse event; AESI = adverse event of special interest; CMI = cell mediated immunity; CRF = case report form; d = day; ELISA = enzyme-linked immunosorbent assay; EOT = end of trial; h = hour(s); IMP = investigational medicinal product; inj. = (IMP) injection; NAAT = nucleic acid amplification-based test; NATAB = neutralizing antibody titers and antibody binding; SAE = serious adverse event; SRC = safety review committee; SARS-CoV-2 = the virus leading to COVID-19; SoA = schedule of activities; WOCBP = women of childbearing potential.

BioNTech SE	Clinical Trial Protocol	Page 15 of 91 Version: 4.0
Confidential	BN1162-14	Date: 20 JAN 2022

Table 2a: Schedule of events for Immunology Subgroup of Group B transplant subjects (injection 2)

Activity	Visit 8	Visit 9	Visit 10	Visit 11 ^g	Visit 12 ^g	Early termination
Week(s) (post-Dose 2)		1	4	12	26	
Day (post-Dose 2)	1	8+2	29±7	85±10	182±20	
	(3 to 7 months post inj. 1; pre-dose except inj. 2)	(~7 d post inj. 2)	(~28 d post inj. 2)	(~3 months post inj. 2)	(~6 months post inj. 2 EOT Visit)	
Collect informed consent						
Assess inclusion/exclusion criteria compliance						
Collect demographic and medical history						
Physical examination	X ^a	X ^a			X a	X a
Vital signs, body weight ^b	X c					
Urine pregnancy test for WOCBP	Х					Х
Blood draw for hematology testing (up to 3 mL) $^{\rm d}$	Х	Х	Х			
Allocation to IMP						
IMP injection, then observe subjects for ~1 h	Х					
Subject hotline availability	=>	=>	=>	=>	End	(End)
Oral swab for NAAT-based SARS-CoV-2 testing for surveillance	×	х	х	х	Х	×
Oral swab for SARS-CoV-2 sequencing ^e	Х	Х	х	Х	Х	Х
Blood draws for NATAB and nucleocapsid protein testing (15 mL)	×	х	х	х	х	x

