9.4.1 General considerations

In general, data will be summarized by groups (i.e., two randomized subgroups in Group A and non-randomized Group B with an immunology subset). Data may be pooled with trials BNT162-01 and BNT162-04.

Continuous variables will be summarized by group using the following descriptive statistics: number of subjects (n), mean, standard deviation, median, minimum, and maximum.

Categorical variables will be summarized by group presenting absolute and relative frequencies (n and %) of subjects in each category.

Baseline is defined as last available value prior to first dose of IMP.

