6.1.2. Definitions and derivations

Unscheduled visits

Unscheduled visits will not be included in the summary tables but will be included in the listings.

Variables

Unless otherwise specified, **baseline** is defined as last value prior to first injection of IMP (Dose 1) given in this BNT162-14 trial on Day 1, including unscheduled visits.

Change from baseline will be calculated as follows:

• Change from baseline = post-baseline assessment value – baseline assessment value.

Duration [days] will be calculated as follows:

• Duration [days] = last observation date – first observation date + 1

Time from first injection (Dose 1) to first reaction will be calculated as follows: Time from first injection to first reaction [days] = first reaction date – date of first injection (Dose 1) + 1

Time from first reaction to last reaction will be calculated as follows:

Time from first to last reaction [days] = last reaction date – first reaction date + 1

Days since last injection will be calculated as follows:

Days since last injection = onset date of AE – date of last injection +1

For conversion of days to months or years the following rules will be applied:

- 1 month = 30.25 days
- 1 year = 365.25 days

Study Day and are defined as follows:

- Study day:
 - If study date < date of first injection (Dose 1), then study day = study date date of first injection
 - If study date >= date of first injection (Dose 1), then study day = study date date of first injection + 1

Fold rise will be calculated as follows:

• Fold rise = post-dose value / baseline value

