6.8.2. Laboratory assessments

Definition

Clinical laboratory data to be summarized includes hematology, clinical chemistry, and urinalysis and will be assessed at the time-points indicated in Tables 1, 2, 2a, and 3 of the protocol.

The following clinical laboratory variables will be assessed:

Hematology

Hemoglobin, hematocrit, red blood cell count, white blood cell count and differential (neutrophils, lymphocytes, monocytes, eosinophils, basophils), platelet count.

Clinical chemistry

Alkaline phosphatase, creatinine, ferritin, C-reactive protein, albumin, alanine aminotransferase, amylase, aspartate aminotransferase, gamma glutamyl transpeptidase, total bilirubin, blood urea nitrogen, glucose, lipase, sodium, potassium, calcium.

Follicle-stimulating hormone: In women only.

Urinalysis

Dipstick: glucose, bilirubin, ketone, specific gravity (1 mL \triangleq 1 g), blood, pH, protein, urobilinogen, nitrite, and leukocytes.

Microscopic urinalysis: If warranted by dipstick results, urine sediment will be microscopically examined for presence of red blood cells, white blood cells, casts, crystals, epithelial cells, and bacteria.

All laboratory tests are classified as normal or lower or higher than reference range (abnormal). All abnormal laboratory tests will be classified by the investigator as clinically significant (CS) or not clinically significant (NCS).

Abnormal lymphocytes data will be categorized as defined in table 7 in the protocol as Grade 1 (mild), Grade 2 (moderate), Grade 3 (severe), and Grade 4 (potentially life-threatening).

Analysis

Clinical laboratory variables at each time-point and its change from baseline to each post-baseline time-point (for continuous variables and if applicable) will be summarized using descriptive summary statistics for each parameter.

Number and percentage of subjects with low, normal and high clinical laboratory values at each time-point will be summarized for each parameter. The same table will be provided for the grading scheme (grades mild, moderate, severe and life threatening) for lymphocytes.

The number and percentage of subjects with CS abnormal, abnormal (NCS), normal and missing values will be summarized for each parameter.

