Clinical laboratory values for each parameter will be summarized using shift tables from baseline to worst post-baseline value with respect to reference range values (low, normal, high), if applicable. Worst post-baseline might be in both directions. Each subject may be counted in the parameter high and in the parameter low category. A subject will only be counted in the normal category if all post-baseline values are normal. If several post-baseline values are considered as worst post-baseline value, the first one is taken.

All clinical laboratory data will be presented in the data listings along with normal ranges abnormal clinical laboratory values will be flagged in the listing.

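### For transplant subjects the SAP has no laboratory baseline for injection 2, so hematology change and worst-value shift tables cannot separate changes before injection 2 from changes after it

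*SAP*

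**What the plan says.** **Baseline.** SAP 6.1.2 says that, unless specified otherwise, baseline "is defined as last value prior to first injection of IMP (Dose 1) given in this BNT162-14 trial on Day 1, including unscheduled visits". Protocol 9.4.1 agrees: "Baseline is defined as last available value prior to first dose of IMP". SAP 6.8.2 specifies no other baseline for laboratory data.

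**Laboratory summaries.** SAP 6.8.2 takes its time points from the protocol schedules; the data "will be assessed at the time-points indicated in Tables 1, 2, 2a, and 3 of the protocol". It plans descriptive statistics for "Clinical laboratory variables at each time-point and its change from baseline to each post-baseline time-point", and "shift tables from baseline to worst post-baseline value with respect to reference range values (low, normal, high), if applicable". In the shift table a subject counts as normal only if every post-baseline value is normal. The low/normal/high counts and the lymphocyte grades are tabulated by time point.

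**Schedule.** Protocol 1.3 has transplant subjects follow Table 2 until injection 2. Table 2 schedules the clinical laboratory panel, hematology included, at Visit 0 only; footnote d allows further draws if clinically indicated. Table 2a then adds a row "Blood draw for hematology testing (up to 3 mL") at Visits 8, 9 and 10. Visit 8 is the day of injection 2, 3 to 7 months after injection 1, with samples taken before the injection.

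**The concern.** Visit 8 supplies a hematology value immediately before injection 2, but the SAP never uses it as a reference for what follows. Under the single baseline it is one more post-baseline value. This has two consequences:

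- Change at Visits 9 and 10 is measured from screening, so it combines the months before injection 2 with the days or weeks after it.
- The shift table takes the worst value over Visits 8, 9 and 10. A subject out of range only at Visit 8 cannot be counted as normal, and the table does not show that the abnormality came before injection 2.

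Protocol 2.2 says that data after injection 2 are meant to support the safety rationale for a fourth vaccination in this population. For hematology, these two summaries do not isolate that period. Adverse events are handled differently: SAP 6.4.3 gives transplant subjects a separate TEAE window after injection 2.

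**Working it through.** The documents state no figure for this point, so there is none to reproduce. The check is interval arithmetic on the schedule.

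**Inputs**
- Visit 0: 1 to 30 days before injection 1 (Protocol Table 2).
- Visit 8: 3 to 7 months after injection 1, before injection 2 (Table 2a).
- Visit 9: Day 8+2 after injection 2, so 7 to 9 days after it. Visit 10: Day 29±7, so 21 to 35 days after it (Table 2a).
- One month = 30.25 days (SAP 6.1.2).
- At most 15 transplant subjects (SAP 1.2).

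**Screening to Visit 8**
- Shortest: 1 + 3 × 30.25 = 91.75 days.
- Longest: 30 + 7 × 30.25 = 241.75 days.

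**Length of the change interval from screening**
- Visit 9: 91.75 + 7 = 98.75 to 241.75 + 9 = 250.75 days.
- Visit 10: 91.75 + 21 = 112.75 to 241.75 + 35 = 276.75 days.

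**Share of that interval before injection 2** = (screening to Visit 8) / (screening to Visit 8 + days since injection 2)
- Visit 9: 91.75/(91.75 + 9) = 91% to 241.75/(241.75 + 7) = 97%.
- Visit 10: 91.75/(91.75 + 35) = 72% to 241.75/(241.75 + 21) = 92%.

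The SAP baseline may also be an unscheduled draw before injection 1. Even one taken on Day 1 leaves at least 90.75/99.75 = 91% at Visit 9 and 90.75/125.75 = 72% at Visit 10 before injection 2.

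**With Visit 8 as reference** the intervals are 7–9 days at Visit 9 and 21–35 days at Visit 10, all after injection 2.

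**Shift table.** One of the three pooled scheduled draws (Visit 8 of 8, 9 and 10) precedes injection 2. How many subjects this could affect depends on an out-of-range rate and a within-subject correlation that the documents do not give. As an assumption only, let each draw have an independent chance q of being out of range in a given direction for one parameter. The chance of being flagged solely because of Visit 8 is q(1−q)²:
- q = 2.5%: 0.0238, or 0.4 of 15 subjects.
- q = 5%: 0.0451, or 0.7 of 15.
- q = 20%: 0.128, or 1.9 of 15.

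At a given q these are upper bounds if repeat draws in a subject are positively correlated; at full correlation the number is zero. They count any out-of-range value, whereas a shift also depends on baseline status.

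**The case against.** The case for leaving the SAP as it stands has several parts, and much of it is right.

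- **Visit 8 is properly post-baseline.** It follows injection 1 of the same product, and both documents define one baseline before the first dose. A reader might infer that Visit 8 should be removed from all post-baseline derivations. The documents do not support that: it is the only scheduled hematology between the two injections, and Protocol 9.4.5 calls for change to each post-baseline time point.
- **Hematology is not confined to the period around injection 2.** A reader of Table 2a alone might think so, but Table 2 includes hematology at screening and allows clinically indicated draws. Only the scheduled post-baseline draws cluster around injection 2.
- **Nothing is attributed to the vaccine.** A reader might infer that drift would be reported as a vaccine effect. The SAP is descriptive, does no testing and assigns no laboratory change to a dose. The documents give no data on drift either.
- **Several outputs already show Visit 8 separately.** The by-time-point tables, lymphocyte grades included, use no baseline, and the listings give every value. With at most 15 subjects, a patient reader can follow Visits 8, 9 and 10 by hand. If the same subjects have all draws, subtracting the mean change at Visit 8 from that at Visit 9 or 10 gives the mean change since injection 2.

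This narrows the point without removing it. The spread, median and extremes of the change since injection 2 cannot be recovered from the planned change table. The shift table cannot be unpooled without going back to the listings.

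**Conclusion.** The point holds for two summaries in SAP 6.8.2: change from baseline at Visits 9 and 10, and the worst-value shift table, both for Group B transplant hematology. Most of each change interval lies before injection 2 (91–97% at Visit 9, 72–92% at Visit 10), and one of three pooled scheduled draws precedes it. These tables therefore cannot distinguish changes before injection 2 from changes after it. By-visit tables and listings are sound.

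The interval figures assume visits within their windows, the SAP's month conversion and screening as the baseline draw. They describe elapsed time, not the size of any change in counts; that size is unknown. The subject counts shown for the shift table are illustrations under assumed rates. This is a cheap improvement to a descriptive safety analysis in at most 15 subjects. It does not affect the trial's other conclusions.

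**What to change.** In SAP 6.8.2, keep the existing baseline and the overall change and shift tables. For Group B transplant subjects, add:

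- a second baseline, defined as the last value before injection 2 (the Visit 8 pre-dose draw);
- change from that baseline to Visits 9 and 10;
- an injection-2 shift table from that baseline, with a worst-value window of Visits 9 and 10 only.

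Keep Visit 8 against screening as its own row, so that the period after injection 1 stays visible. The cost is one derived baseline flag, a few extra tables for at most 15 subjects and a short SAP wording change. No new samples, visits or data are needed.

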6.8.3. Vital signs

Definition

Vital sign parameters to be summarized include body temperature [°C], pulse rate [bpm], respiratory rate [breaths per minute], and systolic and diastolic blood pressure [mmHg] and will be assessed at the time-points indicated in Tables 1, 2, 2a, and 3 of the protocol. Only body temperature assessed at the vital signs assessments will be shown (body temperature will also be assessed in the subject diary but will not be considered for the descriptive analysis of body temperature). Normal ranges of the vital sign parameters are given in Table 3. If a value is out of range, it is categorized as CS or NCS in the CRF.

Parameter	Range
Systolic blood pressure	90 to 140 mmHg
Diastolic blood pressure	<= 90 mmHg
Pulse rate	50 to 100 beats per minute (bpm)

Table 3: Normal ranges for vital signs

Respiration rate	8 to 20 breaths per minute
Temperature (where applicable)	35.5 to 37.5°C

Analysis

Vital sign variables at each time-point, and its change from baseline to each postbaseline time-point will be summarized using descriptive summary statistics for each parameter.

Vital sign values for each parameter will be classified as normal/abnormal according to whether the value is within or outside of the reference range for that parameter (see Table 3). The number and percentage of subjects with CS abnormal, abnormal (NCS), normal and missing values will be summarized for each parameter.

All vital sign data will be presented in the data listings. Abnormal vital signs values and clinically significant vital sign abnormalities will be flagged in the listing.

6.8.4. Further safety data

Physical examination and the SARS-CoV-2 testing results will be listed.

7. Supporting documentation

7.1. Appendix 1: Changes to protocol-planned analyses

Instead of AEs by grade, the overall AE table will include AEs with Grade \geq 3.

7.2. Appendix 2: List of abbreviations

Abbreviation/Term	Explanation
AE	Adverse event
AESI	Adverse event of special interest
ATC	Anatomical Therapeutic Chemical
bpm	Beats per minute
С	Celsius
CD	Cluster of differentiation
CI	Confidence interval
CMI	Cell-mediated immune testing
CRF	Case Report Form
COVID-19	Coronavirus Disease 2019
CS	Clinically significant
DMC	Data Monitoring Committee
ELISA	Enzyme-linked immunosorbent assay
FDA	Food and drug administration
GMFR	Geometric mean fold rise
GMT	Geometric mean titer
h	Hour(s)
IMP	Investigational medicinal product
LLOD	Lower limit of detection
LLOQ	Lower Limit of quantification
max	Maximum
MedDRA®	Medical Dictionary for Regulatory Activities
min	Minimum
min	Minute
mL	Millilitre
mmHg	Millimeter of mercury

modRNA	Nucleoside-modified messenger RNA
Ν	Number of subjects
n	Number of observations
NCS	Not clinically significant
PT	Preferred term
pVNT	Pseudovirus neutralization test
RBD	Receptor binding domain
SAF	Safety analysis set
SAP	Statistical analysis plan
SARS-CoV-2	The virus leading to COVID-19
SAS	Statistical analysis software
SCR	Screened set
SD	Standard deviation
SOC	System organ class
SOP	Standard operating procedures
S protein	SARS-CoV-2 spike protein
S1	Subunit produced after the SARS-CoV-2 S protein is cleaved by host proteases
SRC	Safety Review Committee
SUSAR	Suspected unexpected serious adverse reaction
TEAE	Treatment emergent adverse event
TESAE	Treatment emergent serious adverse event
ULOD	Upper limit of detection
ULOQ	Upper limit of quantification
VNT	Virus neutralization test
WHO	World Health Organization Drug Dictionary

7.3. Appendix 3: Reporting conventions

SAS version 9.4, or higher, will be used to produce all tables, listings, and figures.

For summary statistics, the mean, median, and SD will be displayed to one decimal place greater than the original value. Minimum and maximum will be reported to the same decimal places as the original value. Percentages will be presented with no decimal places. Rounding will be done as follows:

Numbers with first digit after the decimal point \geq 5 will be rounded up to the next integer. All others will be rounded down to the next integer.

The antibody response is defined as the geometric mean of the antibody titer replicates. Therefore, summary statistics and minimum and maximum are displayed with the same number of decimals for antibody response and its fold rise.

8. References

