1.1. Objectives and endpoints

Table 2: Objectives and endpoints

Objectives	Endpoints
Primary	
To determine the safety and tolerability of one or two boosting doses of Comirnaty or one dose of BNT162b2s01 in BNT162- 01 trial subjects, or two boosting doses of Comirnaty in BNT162-04 trial subjects.	 For all Group A and Group B subjects: The proportion of subjects in each treatment group with at least one SAE or the proportion of AESIs occurring up to 26 weeks after the first IMP injection. For Group A and a selected subset of Group B subjects: The frequency of solicited local reactions (pain, tenderness, erythema/redness, induration/swelling) at the injection site recorded up to 7 days after each IMP injection. The frequency of solicited systemic reactions (vomiting, diarrhea, headache, fatigue/tiredness, fever, chills, nausea, new or worsened muscle pain, new or worsening joint pain) recorded up to 7 days after each IMP injection. The proportion of subjects with at least one unsolicited TEAE occurring up to 28 days after IMP injection in each treatment group.

Objectives	Endpoints
Secondary	
To describe changes in SARS-CoV-2 neutralizing antibody titers from baseline to reference and SARS-CoV-2 variant B.1.351.	 For Group A and Group B subjects (except transplant subjects): Antibody titers to recombinant S1 and RBD protein derived from reference and SARS-CoV-2 variant B.1.351** will be assessed at baseline (Day 1) and then Day 8, Weeks 3*, 4, 7*, 12, and 26: Neutralizing antibody titers. Antibody titers (ELISA). SARS-CoV-2 functional cross-neutralization of variant B.1.351** to reference strain.
	 * Group B only ** Group A only For Group B transplant subjects only: Antibody titers to recombinant S1 and RBD protein derived from SARS-CoV-2 will be assessed at baseline (Day 1) and then Day 8, Weeks 4, 12, and 26 post Dose 1, and at Dose 2 (Day 1) and then Day 8, Weeks 4, 12 and, 26 post Dose 2: Neutralizing antibody titers Antibody titers (ELISA)
Exploratory	

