	Group B immunology subset and will receive one injection of Comirnaty [®] which could be potentially followed 3 to 7 months afterwards by a second injection of Comirnaty [®] . This group will be referred to as Group B transplants. Subjects not eligible during this period due to any medical reason (e.g., breakthrough infection causing investigational medicinal product delay decision from the investigator) will not receive the 4 th dose in this trial. Dose : 30 µg of Comirnaty [®] or BNT162b2s01 Dosing regimen: Group A: One (at Day 1) intramuscular injection with 30 µg of either Comirnaty or BNT162b2s01. Group B: Two (at Day 1 and Day 21) intramuscular injections with 30 µg of Comirnaty, except Group B transplant subjects. Group B transplant subjects: Two intramuscular injections of 30 µg of Comirnaty, with injection 2 administered 3 to 7 months after injection 1 (Day 1). The planned time points for injection of the investigational medicinal product for Groups A and B are provided in the Schedule of Activities in the protocol (Section 1.3)
	Administration route: Intramuscular
Treatment and study duration	In total, the planned trial duration for a subject in this trial is approximately 30 weeks (≤4 weeks of screening and ~26 weeks follow-up).
Planned number of subjects	The maximum number of subjects in Group A will be 90 (including up to 15 HIV-positive subjects) and in Group B will be 459 (including up to15 transplant subjects). A subset of Group B (n=129) will be asked to participate in an immunology subset evaluation.
Randomization and blinding	Subjects in Group A will be randomized in a 2:1 ratio to either BNT162b2s01 or Comirnaty [®] . All subjects in Group B will receive at least one injection of Comirnaty [®] . They will not be randomized. The study is open-label.

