6.3. Baseline characteristics

6.3.1. Demographics

Demographic and baseline variables will be summarized for subjects in the SAF analysis set. Age (calculated as age [years] + age_months [months] /12) and weight [kg] will be summarized as continuous data.

Additionally, age will be summarized with the following categories:

• 18 to <= 64 years

- 65 to <= 84 years
- >=85 years

Gender (male or female), ethnicity (Hispanic or Latino, Not Hispanic or Latino, Not reported, Unknown), race (White, Black, or African American, Asian, American Indian or Alaska Native, Native Hawaiian or Other Pacific Islander, Not reported, Unknown, Other) and country will be summarized as categorical data.

A listing of demographic data will be provided.

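### SAP 6.3.1 age bands leave ages such as 64 years 6 months in no category; the month length and whole-number percentages need small corrections too (minor)

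*SAP*

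**What the plan says.** **Age.** Protocol 10.11.1 collects age in years and months. SAP 6.3.1 defines it as "Age (calculated as age [years] + age_months [months] /12", which gives a fractional value. The same section then lists three categories: "18 to <= 64 years", "65 to <= 84 years" and 85 years or older. It does not say that age is truncated to completed years before banding.

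**Month length.** The conversion list in SAP 6.1.2 has "1 month = 30.25 days", followed by a year of 365.25 days.

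**Percentages.** SAP 7.3 says "Percentages will be presented with no decimal places". A first decimal of 5 or more rounds up, and for the rest: "All others will be rounded down to the next integer". One primary endpoint for all Group A and Group B subjects (SAP 1.1) is "The proportion of subjects in each treatment group with at least one SAE or the proportion of AESIs occurring up to 26 weeks", counted from Dose 1. SAP 1.2 gives the maximum size: "in Group B will be 459 (including up to15 transplant subjects". SAP 6.1.1 uses the analysis-set N as the default denominator, shows the count beside the percentage, and makes exact Clopper-Pearson intervals optional.

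**The concern.** The age rule is the main point, because it is wrong as written. A continuous age cannot be sorted completely into bands whose upper limits stop at a whole birthday while the next band starts a full year later. Subjects with a valid recorded age would fall between categories. What is at stake is the completeness of a baseline table.

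The month rule contradicts its neighbour in the same list. It would slightly inflate any interval converted from days to months.

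The percentage rule matters because Group B is the largest group, and events such as myocarditis or anaphylaxis may occur in only one or two subjects. The printed proportion, which is the endpoint itself, could then read as zero when it is not.

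**Working it through.** **1. Age bands.** Inputs: the SAP 6.3.1 formula, age = years + months/12, and its three bands.

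- 64 y 0 mo = 64.000: first band.
- 64 y 1 mo = 64 + 1/12 = 64.083, and 64 y 11 mo = 64 + 11/12 = 64.917. Both exceed 64 and are below 65: no band.
- 84 y 1 mo = 84.083 and 84 y 11 mo = 84.917. Both exceed 84 and are below 85: no band.
- Testing every age from 18 y 0 mo to 99 y 11 mo finds 11 + 11 = 22 unclassified values, and no others.
- With bands 18 to <65, 65 to <85 and >=85, none is left unclassified.

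The protocol enrols adults from 18 years and states no upper age limit (sections 1.1 and 5.1), so both gaps can occur.

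**2. Month length.** Inputs: 30.25 and 365.25 days (SAP 6.1.2).

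- 12 × 30.25 = 363 days, not 365.25.
- 365.25 / 12 = 30.4375 days, so the SAP's year does not reproduce the stated 30.25.
- 30.25 / 30.4375 − 1 = −0.62%.
- At 18 months: 18 × 30.25 = 544.5 days against 18 × 30.4375 = 547.9 days. Dividing, 547.875 / 30.25 = 18.11, so an 18-month interval is overstated by about 0.11 month.

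**3. Percentages.** Inputs: the SAP 7.3 rounding rule; N = 459 for Group B at its maximum, or 459 − 15 = 444 without transplant subjects.

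| Subjects with event, N = 459 | % | Printed under SAP 7.3 | To one decimal | Exact 95% CI, to one decimal |
|---|---|---|---|---|
| 0 | 0.000 | 0 (0%) | 0.0% | 0.0 to 0.8% |
| 1 | 0.218 | 1 (0%) | 0.2% | 0.0 to 1.2% |
| 2 | 0.436 | 2 (0%) | 0.4% | 0.1 to 1.6% |
| 3 | 0.654 | 3 (1%) | 0.7% | 0.1 to 1.9% |

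At N = 444, one and two subjects give 0.225% and 0.450%, which also print as 0%. If interval limits follow the same whole-number rule, zero and one subject both show 0% (0 to 1).

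Threshold: x subjects print as 0% when 100x/N < 0.5, that is when N > 200x. So N must exceed 200 for one subject and 400 for two. The smaller groups are not affected: 1/129 = 0.8% prints 1% (immunology subset), 1/90 = 1.1% prints 1% (Group A), and 1/15 = 6.7% prints 7% (transplant subjects).

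**The case against.** **Age.** SAP 6.3.1 attaches the fractional formula to the summary of age as a continuous variable and introduces the bands separately, in the usual completed-years format. A programmer might well truncate first, and then nobody is lost. No planned subgroup in SAP 5.3 uses age, and SAP 6.1.1 allows a missing category. This limits the damage but does not remove the defect: the only age the section defines is fractional, and placing a recorded age under missing would itself be an error.

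**Percentages.** A reader might infer that a rare AESI would disappear from the report. The documents do not support that. SAP 6.1.1 and 6.4.3 require the number as well as the percentage, and SAEs and AESIs are also listed, so 1 (0%) is distinguishable from 0 (0%). The figure of 459 is a maximum, and the problem vanishes at 200 or fewer. What remains is that the percentage and its distinction from zero are lost.

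**Month length.** A reader might infer that subjects near the 18-month limit, or near the 7-month end of the interval between transplant injections, would be recorded as out of window and hence as major deviations. Nothing in the documents applies the constant that way. The 18-month limit is an inclusion criterion (protocol 5.1). The 3-to-7-month interval is part of the dosing regimen, not an eligibility criterion. Major deviations are identified by medical review (SAP 5.2). SAP 6.8.1 summarises injection intervals without stating a unit, so it is not even certain that an output in months will exist. Only the internal contradiction stands.

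**Conclusion.** The point holds, at minor severity. The age bands are wrong as written: 11 of the 12 month values in each of two years of age belong to no category. How many subjects this touches cannot be estimated, because the documents give no age distribution. The finding rests on the literal text and falls away in practice if completed years are used.

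The 30.25-day month conflicts with the SAP's own year by about 0.6%, with no demonstrated effect on eligibility, deviations or any named output. Whole-number percentages make a primary Group B SAE or AESI proportion of one or two subjects look like zero if enrolment is near 459 (for one subject, above 200), while the count stays visible. None of the three changes a conclusion that the trial is designed to draw, since no hypothesis is tested.

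**What to change.** Make three one-line changes to the SAP:

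- **6.3.1:** use bands 18 to <65, 65 to <85 and >=85 years. Alternatively, keep the present bands and state that they apply to completed years.
- **6.1.2:** set 1 month = 30.4375 days, so that twelve months equal the SAP's year.
- **7.3:** print percentages to one decimal, and give the exact 95% confidence intervals for the SAE and AESI proportions to one decimal as well.

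The cost is editorial: no change to design, data collection or clinical conduct, and a small adjustment to table specifications.
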